9.3.2 Responder Status Endpoints

Different efficacy responder statuses will be defined based on the following methods [4, 10]:

- Responder at $\geq 30\%$ Pain Reduction:
 - Subjects achieving ≥30% pain reduction on the mean NRS score assessing average pain intensity in the past 24 hours from baseline to Week 4 analysis visit and the subjects must complete the study. Subjects who do not have an analysis visit Week 4 mean NRS score assessing average pain intensity in the past 24 hours will be set to a non-responder.

- Responder at ≥50% Pain Reduction:
 - Subjects achieving ≥50% pain reduction on the mean NRS score assessing average pain intensity in the past 24 hours from baseline to Week 4 analysis visit and the subjects must complete the study. Subjects who do not have an analysis visit Week 4 mean NRS score assessing average pain intensity in the past 24 hours will be set to a non-responder.
- Responder at ≥30% Pain Reduction and Week 4 PGI-C Improved Score:
 - Subjects achieving ≥30% pain reduction on the mean NRS score assessing average pain intensity in the past 24 hours from baseline to Week 4 analysis visit and the subjects must complete the study. Subjects who do not have an analysis visit Week 4 mean NRS score assessing average pain intensity in the past 24 hours will be set to a non-responder.
 - o In addition, to be classified as "responders" subjects must have an analysis visit Week 4 PGI-C score of 1 (Very Much Improved) or 2 (Much Improved). Otherwise, those subjects will be set to non-responders.

The percent change from baseline that is \leq -30.0% is equivalent to \geq 30% pain reduction. Subjects with a calculated mean NRS score assessing average pain intensity in the past 24 hours at analysis visit Week 4 will be provided in a figure based on their percent change from baseline values. The horizontal axis displays a range of percentage-reductions from baseline at Week 4 in the mean NRS score assessing average pain intensity in the past 24 hours and the vertical axis displays the percentage of subjects achieving each of those levels of improvement. The horizontal axis will range from 0% to 100% in percentage-reductions and will not plot subjects with percentages below 0% (i.e. subjects that showed worse pain at Week 4 and the percentage change from baseline \geq 0%).

Frequency distributions, odds ratio, and relative risk analyses described in Section 5.3.5.5 will be used to summarize the responder status endpoints.

9.3.3 Number of Days to Responder Status

The number of days [4] to responder status will consider any 4 consecutive days between Study Day 1 and 28. If any of the 4-day means for NRS score assessing average pain intensity in the past 24 hours at show a $\geq 30\%$ pain reduction, then the first study day within the 4-day interval will be the number of days to responder status. Individual scores on the first study day within the 4-day interval may be missing or <30% pain reduction as long as the 4-day mean is $\geq 30\%$. A maximum of 1 missing value may be present in the mean calculation if at least 3 scores are present.

The number of days using $\geq 50\%$ pain reduction will also be calculated using the same methods. The number of days to responder status will be based on the observed daily pain scores and will not use any imputation methods for missing data described in Section 9.1.3. Cox proportional hazards modeling analyses described in Section 5.3.5.4 will be used for the number of days in each responder definition. Additionally, a Kaplan-Meier probability plot will be created for each planned treatment arm and number of days to responder status.

9.3.4 Number of Days to Sustained Pain Reduction

If a subject reaches a responder status at any point of the study as defined in Section 9.3.3, the following additional conditions will also need to be met in order for the subject to be considered as sustaining pain reduction:

Protocol No.: NYX-2925-2001

- At least 8 days from the onset of the response to the last collected pain score that is \leq Study Day 28.
 - o Study Day 21 is the latest possible day for sustained pain reduction if the study day NRS score assessing average pain intensity in the past 24 hours was collected.
- The responder status endpoint of interest stated in Section 9.3.2 must by met at the Week 4 analysis visit.
 - Responder at ≥30% Pain Reduction
 - o Responder at ≥50% Pain Reduction
- Once the responder status has been met, the remainder of the study days after the last day in the 4-day interval until Study Day 28 will calculate the overall remaining mean for NRS score assessing average pain intensity in the past 24 hours. If the overall remaining mean score shows a pain reduction \geq to the responder status (i.e. \geq 30% or \geq 50%), then this criteria of the sustained pain reduction will be met.

A frequency distribution of these categories will be summarized:

- >30% Pain Reduction Status
 - Never Reached
 - o Reached, but did not Sustain
 - Reached and Sustained at Mean Analysis Visit Week 4 (Responder Endpoint)
- >50% Pain Reduction Status
 - Never Reached
 - o Reached, but did not Sustain
 - Reached and Sustained at Mean Analysis Visit Week 4 (Responder Endpoint)

The number of days of onset to sustained pain reduction will be summarized using descriptive statistics. The same Cox proportional hazards modeling analyses and Kaplan-Meier probability plot described in Section 9.3.3 will be applied to sustained pain reduction data. The number of days to sustained pain reduction will be based on the observed daily pain scores and will not use any imputation methods for missing data described in Section 9.1.3.

9.4 Summary of Efficacy Analyses

The table below describes the p-value analyses preformed on the different types of efficacy data for this study:

Efficacy Data	ANCOVA	Repeated Measures	Hazard Modeling	Chi- Square
Mean Change from Baseline NRS Score Assessing Average Pain Intensity in the Past 24 Hours at Week 4	X			
Mean Change from Baseline NRS Score Assessing Average Pain Intensity in the Past 24 Hours at Weeks 1, 2, 3, and 4	X	X		
Mean Change from Baseline NRS Score Assessing Worst Pain Intensity in the Past 24 Hours at Week 4	X			

Protocol No.: NYX-2925-2001

Efficacy Data	ANCOVA	Repeated Measures	Hazard Modeling	Chi- Square
Mean Change from Baseline NRS Score Assessing Worst Pain Intensity in the Past 24 Hours at Weeks 1, 2, 3, and 4	X	X		
Mean Change from Baseline NRS Score Assessing Average Pain upon Walking Intensity in the Past 24 Hours at Week 4	X			
Mean Change from Baseline NRS Score Assessing Average Pain upon Walking Intensity in the Past 24 Hours at Weeks 1, 2, 3, and 4	X	X		
PGI-C				X
SF-MPQ-2	X			
Norfolk QOL-DN	X			
ISI	X			
HADS	X			
DSIS	X	X		
BPI-DPN	X			
Responder Status Endpoints				X
Number of Days to Responder Status			X	
Number of Days to Sustained Pain Reduction			X	

10. Safety Analyses

10.1 Adverse Events

Treatment-emergent adverse events (TEAEs) will be those occurring during or after administration of the first dose of study drug until 30 days after the final dose of study drug. Due to the nature of this study, the date and time of first dose of study drug was not collected on the CRF. Therefore, the following algorithm will be used to determine if the adverse events are treatment-emergent:

- Earliest Possible AE Start Date ≥ Baseline Visit and Study Drug Dispensation and
- Latest Possible AE Start Date ≤ 30 Days After the Final Dose of Study Drug

Adverse events that started on the Baseline Visit (Study Day 1) that are the result of abnormal clinically significant electrocardiograms (ECGs) or clinical laboratory tests collected prior to study drug dispensation will not be considered TEAEs.

The following System Organ Class (SOC) AEs for abnormal clinically significant clinical laboratory tests will be reviewed to determine if the AE is not treatment-emergent:

- Investigations
- Infections and infestations (with the Preferred Term = "Urinary tract infection")

AEs that started prior to first dosing of study drug, but become worse in severity after receiving study drug will be considered treatment-emergent. The determination of whether or not an adverse event is classified as "treatment emergent" (i.e. TEAE) is not dictated by the classification of "relationship to study drug" collected on the CRF, but rather by the temporal relationship of the adverse event to the administration of study drug.

A related study drug TEAE is defined as any TEAE with at least a possible relationship to the study drug as assessed by the investigator or that is missing the assessment of causal relationship whose relationship to the study drug could not be ruled out. Relationships of "possibly related", "probably related", or missing are collected on the CRF, then those adverse events will be considered related study drug TEAEs. If the "unrelated" or "unlikely related" are collected on the CRF, then those adverse events will be considered not related study drug TEAEs.

Severity is assigned to each adverse event collected on the CRF. Maximum severity has the following order: "life threatening", "severe", "moderate", and "mild" as possible collection options on the CRF. A missing severity will be treated as "unknown" for analysis purposes.

All adverse events will be coded and summarized by System Organ Class (SOC) and Preferred Term (PT) based on Medical Dictionary for Regulatory Activities (MedDRA) version 19.0 coding dictionary. This data will be summarized in a frequency distribution. Subjects may have more than one TEAE record per SOC and PT. At each level of subject summarization, a subject will be counted once if he/she reports one or more TEAE record at that specific level. For tables summarized by SOC and PT, the events will be displayed in the order of descending frequency counts for all treatments by SOC and then PT within SOC.

The number of subjects with at least one of the following adverse events, percentages for each category by treatment, and the number of total events will be included in an overall treatment-emergent adverse events summary table:

- Any TEAEs
- Related TEAEs
- Maximum Severity TEAEs
- Serious TEAEs
- Related, Serious TEAEs
- TEAEs Leading to Study Discontinuation
- Related TEAEs Leading to Study Discontinuation
- TEAEs Leading to Death

Summaries including the number of subjects and percentages of the following adverse events by SOC and PT will be provided:

- Any TEAEs
- Related TEAEs
- Maximum Severity TEAEs

- Serious TEAEs
- TEAEs Leading to Study Discontinuation

Additionally, TEAEs will be summarized by descending frequency counts of PT for all treatments. All adverse event data collected will be provided in subject listings. Subset subject listings will also be provided by serious treatment-emergent adverse events and deaths; by treatment-emergent adverse events leading to study discontinuation; any adverse events that are not considered to be treatment-emergent; and by adverse events leading to study discontinuation that are not considered to be treatment-emergent.

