- m) Instruct study participants to bring all used and unused investigational product and rescue medication to each visit for compliance monitoring.
- n) Phone call will be made weekly during weeks with no study visits, to reinforce diary completion.
- o) Weekly phone calls will be made during weeks with no study visits, to assess adverse events.

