9.4.2 Recording Adverse Events

A "pre-existing" condition is one that is present before investigational product dosing and is reported as part of the subject's medical history. Pre-existing conditions should be reported as an adverse event only if the frequency, intensity, or character of the pre-existing condition worsens during the course of the study. Adverse events will be collected from the time the informed consent is signed to the end of the subject's participation in the study.

Subjects should be instructed to report all potential adverse events to the investigator, and, queried in a non-leading manner, without specific prompting (e.g., "How are you feeling?"). The site study staff should assess emerging symptoms of dissociative reaction similar to those caused

by NMDA antagonists including memory impairment, disturbance in time, body or environmental perception, stilted speech, emotional withdrawal, impaired coordination, motor retardation, bizarre reasoning or illusory experiences in any sensory perception, or confused state; such symptoms may be captured as adverse events.

To avoid vague, ambiguous, or colloquial expressions, all adverse events should be recorded in standard medical terminology rather than in the subject's own words. Each adverse event will also be described in terms of duration (start and stop date), severity, relationship to investigational product, action(s) taken, and outcome. Diagnoses (rather than symptoms) should be recorded wherever possible.

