12.6.1 Adverse Events

A TEAE is defined as an adverse event with an onset that occurs after receiving investigational product, or a continuing adverse event diagnosed prior to the date of first dose of investigational product, which increases in severity after the start of dosing. Adverse events will be categorized by system organ class and preferred term with the Medical Dictionary for Regulatory Activities.

Summary tables for TEAEs will include number and percent of subjects experiencing TEAEs by system organ class and preferred term. If a subject has more than 1 TEAE that codes to the same preferred term, the subject will be counted only once for that preferred term. Similarly, if a subject has more than 1 TEAE within a system organ class category, the subject will be counted only once in that system organ class category.

The following TEAE summaries will be provided for the Screening Period and Treatment Period (including Follow-Up):

- Overall summary of TEAEs
- TEAEs by system organ class and preferred term
- Drug-related TEAEs by system organ class and preferred term
- TEAEs by system organ class, preferred term, and severity

Serious TEAEs and TEAEs leading to investigational product discontinuation will be identified.

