5.5.3 Missing or Partial Dates

Adverse Event Start Dates:

- Method 1 Earliest Possible Start Date:
 - o If any combination of the year, month, and/or day are missing then the start date will be set to the earliest possible date that is \geq to the screening date.
- Method 2 Latest Possible Start Date:
 - If any combination of the year, month, and/or day are missing then the start date will be set to the latest possible date that is \leq to the latest possible adverse event end date. If the adverse event is ongoing after the final visit for the subject, then the final visit date will be used.

Prior/Concomitant Medications Start Dates:

- Method 1 Earliest Possible Start Date:
 - o If any combination of the year, month, and/or day are missing then the start date will be set to the earliest possible date that is \geq to the subject's date of birth.
- Method 2 Latest Possible Start Date:
 - o If any combination of the year, month, and/or day are missing then the start date will be set to the latest possible date that is < to the latest possible medication end date. If the medication is ongoing after the final visit for the subject, then the final visit date will be used.

Adverse Event and Prior/Concomitant Medications End Dates:

- Method 1 Earliest Possible End Date:
 - If any combination of the year, month, and/or day are missing then the end date will be set to the earliest possible date that is \geq to the earliest possible adverse event/medication start date.
- Method 2 Latest Possible End Date:
 - o If any combination of the year, month, and/or day are missing then the end date will be set to the latest possible date that is \leq to the subject's final visit date. If the adverse event/medication is ongoing after the final visit for the subject, then the final visit date will be used.

Medical History Disease Onset Dates:

- If year is missing, then the date will not be imputed.
- If both the month and day are missing, then the date will be imputed as July 1st with the year collected. However, if this imputed date is \geq to the screening date then the imputed date will be the screening date minus 1 day.
- If only the day is missing, then the date will be imputed as the 15th with the year and month collected. However, if this imputed date is \geq to the screening date then the imputed date will be the screening date minus 1 day.

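### The treatment-emergent test uses the earliest possible onset date, so some on-treatment adverse events with incomplete start dates drop out of the TEAE tables

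*SAP*

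**What the plan says.** SAP 10.1 opens by defining treatment-emergent AEs as those arising from the first dose until 30 days after the last. Protocol 12.6.1 agrees: "A TEAE is defined as an adverse event with an onset that occurs after receiving investigational product". Because the date of first dose is not collected, SAP 10.1 replaces this definition with two tests that must both be met. Test 1 is "Earliest Possible AE Start Date ≥ Baseline Visit and Study Drug Dispensation and"; the closing word joins it to test 2, which requires the latest possible start date to be no more than 30 days after the final dose.

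The two dates come from SAP 5.5.3. Under Method 1, if any part of the date is missing, "then the start date will be set to the earliest possible date that is" on or after screening. Under Method 2 the start date is set as late as possible, limited by reference "to the latest possible adverse event end date", or by the final visit if the AE is ongoing. Incomplete end dates are also pushed late: "then the end date will be set to the latest possible date that is" no later than the final visit.

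There is one route back in: "AEs that started prior to first dosing of study drug, but become worse in severity after receiving study drug will be considered treatment-emergent".

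**The concern.** AEs are collected from consent, and screening lasts 1 to 4 weeks, so the earliest possible date for an incomplete onset can easily precede baseline. Test 1 then resolves the doubt in one direction only. An AE that began after dosing can be called pre-treatment, and no rule assigns an ambiguous onset to the treatment period.

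Safety and tolerability is a secondary objective. The planned AE summary tables (14.3.1.1 to 14.3.1.7) are all TEAE tables, and two of them are topline. An AE that fails test 1 is missing from the counts and percentages by arm, which are what a reader uses to judge tolerability by dose. The direction also departs from the SAP's handling of doubt elsewhere. SAP 8.4 lets a medication with ambiguous dates count as both prior and concomitant, and SAP 10.1 treats a missing causality assessment as related.

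**Working it through.** The plan states no figure here, so there is none to reproduce. The check applies the two tests of SAP 10.1 with the dates of SAP 5.5.3.

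**Example.** Screening 24 February, baseline 10 March, true onset 20 March, day not recorded. The earliest possible date is 1 March. That is before 10 March, so test 1 fails and the event is not a TEAE.

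**Which patterns fail test 1**
- Complete date: none.
- Only the day missing: fails if onset is in the calendar month of baseline, unless baseline is the 1st. Onsets in a later month pass.
- Day and month missing: nearly always fails, because the earliest date is the later of 1 January and screening.
- Whole date missing: always fails, because the earliest date is screening.

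**Share lost, only the day missing.** Assumptions: 30-day month, baseline day D uniform on 1 to 30, onset uniform over n days from baseline, no worsening. For D = 2 to 30, the onset days still in the baseline month number min(n, 31 − D). For D = 1 none is lost.
- n = 35: (29 + 28 + … + 1) / (30 × 35) = 435 / 1050 = 0.414
- n = 28: (28 + 28 + 27 + … + 1) / (30 × 28) = 434 / 840 = 0.517
- n = 14: (16 × 14 + 13 + 12 + … + 1) / (30 × 14) = 315 / 420 = 0.750

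**Calendar run.** Assumptions: every baseline date from 1 August 2017 to 15 October 2018, last dose Day 28, final visit Day 35.

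| Missing part of start date | Onset Days 1–35 | Days 1–28 | Days 1–14 |
|---|---|---|---|
| Day | 42.8% | 53.2% | 76.0% |
| Day and month | 95.9% | 96.7% | 98.3% |
| Whole date | 100% | 100% | 100% |

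A separate run over one year of baseline dates (1 August 2017 to 31 July 2018) gave 42%, 95% and 100% for Days 1–35, and 52%, 96% and 100% for Days 1–28. Screening 7 or 28 days before baseline made no difference.

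**Is test 2 responsible?** No. With the last dose on Day 28 its limit is Day 58, and no imputed start can be later than the final visit at Day 35. With the last dose on Day 1, 7, 14, 21 or 28, no on-treatment AE failed test 2 when the final visit was within 30 days of that dose.

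**Share of all on-treatment AEs.** The rate of incomplete dates is not in the documents. Taking 0.414 and assumed rates of 1%, 5% and 10% lacking only the day: 0.414 × 1% = 0.41%; × 5% = 2.07%; × 10% = 4.14%.

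**Effect of using the latest possible start date in test 1.** A true on-treatment onset is never later than its own latest possible date, so test 1 can no longer lose it (0% in every pattern). The price is that some screening AEs are admitted. With only the day missing, the share admitted among onsets in the n days before baseline is the mean of min(n, D − 1) / n:
- n = 7: 182 / 210 = 0.867
- n = 28: 434 / 840 = 0.517

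The calendar run gave 99.1% and 96.7% (n = 7 and 28) with the month also missing, and 100% with the whole date missing. These shares apply to AEs ongoing at baseline, or resolved before it with an end date lacking the same parts. If a complete end date shows resolution before baseline, the share is 0%.

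**Balance of errors.** At an assumed one AE per day before and after baseline, with no end date showing that a screening AE ended before baseline, the misclassified AEs are:

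| Missing part | As written | After change, 1-week screening | After change, 4-week screening |
|---|---|---|---|
| Day | 35 × 0.414 = 14.5 | 7 × 0.867 = 6.1 | 28 × 0.517 = 14.5 |
| Day and month | 35 × 0.959 = 33.6 | 7 × 0.991 = 6.9 | 28 × 0.967 = 27.1 |
| Whole date | 35 | 7 | 28 |

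**The case against.** The strongest reply is that the rule is a coherent convention. It tests both ends of the possible interval and so counts only events certain to lie in the treatment window; with an incomplete date, nobody knows that onset was on treatment. That explains the rule but does not justify it. The definitions it implements turn on onset after dosing, and the SAP resolves comparable doubt inclusively for causality and for medications.

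Second, the effect may be very small. Protocol 9.4.2 requires start and stop dates for each AE. Visits are backed by calls: "Weekly phone calls will be made during weeks with no study visits, to assess adverse events". Most onsets should therefore be known to within about a week, data are monitored for completeness, and the patterns with the largest percentages are the least likely. No safety test depends on the result. Nothing is hidden either: excluded events remain in listings 16.2.7.1 and 16.2.7.3, in 16.2.7.4 if they led to discontinuation, and in 14.3.2.2 if serious. All of this stands, and it is why the point is minor.

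Third, the remedy is not a gain everywhere. With only the day missing and a 4-week screening, the worst case above is 14.5 errors either way. If AEs are more frequent during screening, for example while analgesics are being withdrawn, that case becomes a net loss. This stands too. However, the admitted errors arise before treatment and should be similar across randomised arms, whereas the current rule removes real on-treatment events.

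**Conclusion.** The concern holds, at minor severity. That test 1 can exclude a true on-treatment AE follows directly from SAP 10.1 read with SAP 5.5.3. Given an incomplete start date, the loss is 41% to 75% with only the day missing, depending on the onset window, about 95% to 98% with the month also missing, and 100% with no date. These are shares of AEs with incomplete dates, not of all AEs, and they assume uniform onset and no later worsening. The overall effect cannot be computed from the documents and is probably a few per cent of on-treatment AEs at most. Confidence is high in the mechanism and lower in the net benefit of the remedy when screening is long.

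**What to change.** In test 1 of SAP 10.1 only, replace the earliest possible AE start date with the latest possible one, which Method 2 already derives. An AE is then excluded as pre-treatment only when the recorded parts of its start or end date show that it began before baseline. Keep test 2, the Day 1 ECG and laboratory exception, and the worsening rule. Add a footnote to the TEAE tables giving, by arm, the number of events that qualify only through an incomplete date, so that a reader can subtract them.

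The cost is one phrase in the SAP, one line of derivation code and one footnote, plus the admitted screening AEs quantified above.

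The change leaves one gap. If a Repeat Follow-Up visit falls 35 or more days after the last dose, ongoing AEs would still fail test 2 in about 90–93% of cases with the month missing and 100% with the whole date missing.

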9.4.3.1 Severity of Adverse Events

All adverse events will be assessed for severity, using the following general grading scale:

Mild: Transient or mild discomfort (<48 hours); no medical intervention/therapy required.

Moderate: Mild to moderate limitation in activity – some assistance may be needed; no or minimal medical intervention/therapy required.

Severe: Marked limitation in activity, some assistance usually required; medical intervention/therapy, required hospitalization possible.

Life threatening: Extreme limitation in activity, significant assistance required; significant medical intervention/therapy required, hospitalization, or hospice care probable.

When changes in the severity of an adverse event occur more frequently than once a day, the maximum severity for the experience that day should be noted. If the severity category changes over a number of days, then those changes should be recorded separately (with distinct onset dates).

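### SAP 10.1 classifies adverse events by record start date without linking severity-change records, so a pre-dose event that eases after Day 1 can be tabulated as treatment-emergent and one event can be counted several times in the event total

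*SAP*

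**What the plan says.** **Recording (protocol).** Collection starts before dosing. Section 9.4.2 states: "Adverse events will be collected from the time the informed consent is signed to the end of the subject's participation in the study". Section 9.4.3.1 covers changes in severity. For changes within a day, "the maximum severity for the experience that day should be noted". For slower changes, "If the severity category changes over a number of days, then those changes should be recorded separately (with distinct onset dates". The instruction does not distinguish worsening from improvement.

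**Definition (protocol).** Section 12.6.1 counts an event with onset after dosing. It also counts "a continuing adverse event diagnosed prior to the date of first dose of investigational product, which increases in severity after the start of dosing".

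**Classification (SAP 10.1).** First-dose date and time were not collected, so the SAP uses two date conditions. The lower one is "Earliest Possible AE Start Date ≥ Baseline Visit and Study Drug Dispensation". The upper one requires the start to fall no more than 30 days past the last dose. It then adds: "AEs that started prior to first dosing of study drug, but become worse in severity after receiving study drug will be considered treatment-emergent". The only exclusions concern clinically significant ECG or laboratory findings obtained on Day 1 before dispensation, supported by a review of laboratory-related terms.

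**Counting (SAP 10.1).** A subject counts once at each level of summary. For the overall table, the number of subjects, "percentages for each category by treatment, and the number of total events will be included in an overall treatment-emergent adverse events summary table". The summaries by system organ class and preferred term are described as numbers and percentages of subjects only.

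**Declared changes.** SAP 4.7 lists departures from the protocol. The TEAE definition is not among them.

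**The concern.** The protocol's recording rule makes records out of events, and the SAP's classification rule treats each record's start date as if it were an event's onset. When an event that began in screening drops a severity category after Day 1, the new record starts after baseline and meets both date conditions. The worsening clause brings in pre-dose events that worsen; it removes nothing.

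There are two consequences, of different weight:

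- **False TEAEs.** The improving record can put a subject into the incidence columns for that term, for its organ class and for any TEAE. The count-once rule does not help if this is the subject's only post-dose record at that level.
- **Repeat counting.** A single post-dose event that fluctuates contributes several times to the event total.

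Safety and tolerability are a secondary objective, and no safety data are formally tested, so these descriptive counts carry the adverse event evidence. Tables 14.3.1.1 and 14.3.1.2 are both marked for topline delivery. Screening lasts 1 to 4 weeks and may include analgesic withdrawal, so events still ongoing at Day 1 are plausible.

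**Working it through.** The plan states no figure on this point, so the check applies the two rules to constructed histories. All histories are assumptions.

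**Inputs.** Severity is coded mild 1, moderate 2, severe 3. Records are split as protocol 9.4.3.1 requires. Day 1 is the Baseline Visit and dispensation. The final dose is assumed on Day 28, so the SAP's upper limit is 28 + 30 = Day 58.

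**SAP rule, record by record.** Events = number of records with onset from Day 1 to Day 58. Subject = 1 if there is at least one such record.

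**Linked episode.** Count 1 if the first onset is on or after Day 1, or if the highest post-dose severity exceeds the severity in effect at first dose. Otherwise count 0.

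| History | SAP rule: events (subject) | Linked test | Linked: events (subject) |
|---|---|---|---|
| A: moderate from Day -5, mild from Day 3 | 1 (1) | 1 > 2 is false | 0 (0) |
| B: severe from Day -3, moderate from Day 2, mild from Day 6 | 2 (1) | 2 > 3 is false | 0 (0) |
| C: mild from Day -5, moderate from Day 4 | 1 (1) | 2 > 1 is true | 1 (1) |
| D: mild from Day 3, moderate from Day 6, mild from Day 9 | 3 (1) | onset after Day 1 | 1 (1) |

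Totals: 1 + 2 + 1 + 3 = 7 events in 4 subjects under the literal rule, against 0 + 0 + 1 + 1 = 2 events in 2 subjects when linked. A and B are false TEAEs in both the event total and subject incidence. C is unaffected. D is counted three times in the event total but once in subject n (%), and it appears once, at moderate, in the maximum-severity table. The results depend on the order of the records and on which side of Day 1 each onset falls, not on how long a grade lasts.

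**Which pre-dose severity to compare with.** Take a fifth history: moderate from Day -10, mild from Day -2, moderate from Day 4. The severity in effect at first dose is mild, so 2 > 1 and the event is a TEAE. That agrees with protocol 12.6.1, because severity rose after dosing began. Compared with the highest pre-dose severity, 2 > 2 is false and the event would be lost. The severity in effect at first dose is therefore the right comparator.

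**Which tables are touched.** False TEAEs can reach subject n (%) in both 14.3.1.1 and 14.3.1.2. Repeat counting reaches only the event total, which SAP 10.1 places in the overall table, 14.3.1.1.

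**The case against.** The strongest reply is that the SAP already shows the right intent. Its worsening clause treats an adverse event as keeping its identity when severity changes, and it would be nearly redundant if every change were an independent event with its own start date. The eCRF is not in the documents, and it may hold severity lines under one parent event with one onset date. What stands is that the certainty is limited: with a parent structure, and with the parent's onset used, the problem does not arise. But the protocol asks for distinct onset dates, and the SAP's operative rule is a date rule with no link to a parent.

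The reach is also limited by protocol 9.4.1 and 9.4.2. A condition present before dosing and reported as medical history becomes an adverse event only if it worsens. Such conditions yield no improvement record and are unaffected. Events recorded as adverse events after consent and before dosing remain exposed.

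One can also argue that a split record has a post-dose onset and so meets the first limb of protocol 12.6.1. On that reading the second limb would have little to do. It makes sense only if the unit is the event and not the record.

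Three stronger readings are tempting and are not supported:

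- **Every severity change creates a record.** Changes within a day collapse to the daily maximum.
- **Event totals are inflated in both topline tables.** Table 14.3.1.2 is described as subject counts only.
- **Real dose differences are materially diluted.** If a share q of every arm were wrongly and independently added, a risk difference in any TEAE would shrink by the factor (1 - q). With q assumed as high as 7.5%, a 10-point difference becomes 10 × 0.925 = 9.25 points. Over-inclusion is also the cautious direction when looking for harm.

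**Conclusion.** The defect holds in a bounded form. Read literally, SAP 10.1 counts an improving pre-dose adverse event as treatment-emergent, contrary to protocol 12.6.1 and without declaring a change in SAP 4.7. It also counts a fluctuating post-dose event more than once in the event total of Table 14.3.1.1. The false TEAEs matter more, because they can enter subject incidence. Repeat counting leaves subject n (%) and the maximum-severity summary intact.

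The size cannot be computed, since no adverse event rates are given. A reader might put it at about 2 to 6 subjects per arm. That follows only if 5% to 15% of subjects have an event ongoing at Day 1 and half of these drop a category after dosing: 75 × 0.05 × 0.5 = 1.9 and 75 × 0.15 × 0.5 = 5.6. Neither rate has a source in the documents. For the any-TEAE row even this would be a ceiling, because a subject with another TEAE adds nothing.

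The conclusion assumes that severity changes reach the analysis dataset as separate records with their own start dates, as protocol 9.4.3.1 describes. The primary endpoint is not involved. The rule should be corrected before the safety tables are produced.

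**What to change.** Add to SAP 10.1:

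1. Link severity records with the same subject and preferred term into one episode when the new record starts on the same or the next day after the earlier one stops.
2. Count the episode as a TEAE if its first onset is on or after the Baseline Visit and dispensation, or if any post-dose severity exceeds the severity in effect at first dose. Do not use the highest pre-dose severity as the comparator.
3. Take maximum severity from the post-dose records of the episode.
4. Count each episode once in the event total.

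The existing 30-day limit and the Day 1 ECG and laboratory exclusion can stay. If the eCRF already holds severity lines under a parent event, a sentence saying that the parent's onset is used replaces step 1.

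The cost is brief SAP text and one derivation step in the adverse event dataset, with no new data. There is a small risk of merging two distinct adjacent events that share a preferred term.
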